1.1. Synopsis

Please refer to the Master Protocol LDOS-21-001 for a comprehensive background and rationale for this study of a combination of famotidine and celecoxib as a post-exposure prophylaxis (PEP) for newly-infected COVID-19 patients.

This study (LDOS-21-001-02) is designed to test the efficacy and safety of combinations of two well-understood agents—famotidine and celecoxib. Each of these agents separately demonstrate clinical activity in mitigating COVID-19 disease symptoms or severity, and each of which appear to have separate and complementary mechanisms of action.

Study Description: This is a virtual Phase 2 randomized, placebo-controlled, double-blind study to evaluate the safety and efficacy of the combination of famotidine and celecoxib as a post-exposure prophylaxis (PEP) for newly-infected COVID-19 patients. Qualifying patients will have been confirmed positive for COVID-19 and have symptoms of WHO Ordinal Scale for Clinical Improvement with scores of \leq 3 on the 11–point scale (Table 2), and will be randomly assigned, in a 1: ratio, to one of two regimens, with 659 participants per group, as follows:

• **Group 1 (Study Product)**: 80 mg famotidine (PO) QID + celecoxib 400 mg first dose, followed by 200 mg (PO) BID for 5 days. Following this 5-day period, participants will continue their 80 mg famotidine QID treatment for an additional nine days.

Group 2 (Reference Comparator): Matching placebo for famotidine and celecoxib respectively, QID + BID for five days. Following this 5-day period, participants will continue to receive matching famotidine placebo, QID, for an additional 9 days.

There will be a subsequent follow-up period of 90 days from Baseline (Day 1 of treatment).

Score	Descriptor	Patient State
0	Uninfected; no viral RNA detected	Uninfected
1	Asymptomatic; viral RNA detected	Ambulatory Mild
2	Symptomatic; independent	Ambulatory Mild
3	Symptomatic; assistance needed	Ambulatory Mild
4	Hospitalized; no oxygen therapy	Hospitalized Moderate
5	Hospitalized; oxygen by mask or nasal prongs	Hospitalized Moderate
6	Hospitalized; oxygen by NIV or high flow	Hospitalized Severe
7	Intubation and mechanical ventilation, pO2/FiO2 \geq 150 or SpO2/FiO2 \geq 200	Hospitalized Severe
8	Mechanical ventilation pO2/FiO2 <150 (SpO2/FiO2 <200) or vasopressors	Hospitalized Severe
9	Mechanical ventilation, pO2/FiO2 <150 and vasopressors, dialysis, or ECMO	Hospitalized Severe

Table 2:WHO 11-point Clinical Progression Scale

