Statistical Methods: The study will aim to enroll up to 1465 participants, which assumes a 10% screen failure rate, with a final allocation of 659 participants in the treatment arm and 659 in the control arm.

This sample size of ensures a power of 90% at a 2-sided α of 5%, assuming a 1:1 randomization, a placebo rate of 6% (of participants with at least one COVID-19–related medically attended contact, due to increased symptom severity, or incidence of death due to COVID-19 through Day 30) and an assumed relative risk reduction of 65% to 2.4% in the active treatment arms. The statistical test of the null hypothesis of no between-group difference in proportions, as specified

in the primary endpoint, will be tested using a χ^2 test at a two-sided 5% significance level. An interim analysis for futility will be performed after 50% of participants have completed the primary endpoint assessment at day 30. Safety analyses will be performed on the Safety Population, consisting of all participants who are randomized and received study drug, analyzed by actual treatment arm. A more detailed description of the statistical methods can be found in Section 7.

Protocol Title: A virtual Phase 2 randomized, placebo-controlled, double-blind study to evaluate the safety and efficacy of the combination of famotidine and celecoxib as a post-exposure prophylaxis (PEP) for newly-infected COVID-19 patients.

Short Title: LEAP-CT as a post-exposure prophylaxis for newly-infected COVID-19 patients.

Rationale: Please refer to the Master Protocol LDOS-21-001 for a comprehensive background and rationale for this study of a combination of famotidine and celecoxib as post-exposure prophylaxis (PEP) for newly-infected COVID-19 patients.

Overall Design: This is a Phase 2, randomized double-blind placebo-controlled decentralized virtual study in which outpatient participants, newly diagnosed for COVID-19, will be randomized in a 1:1 ratio to one of two study groups (1 treatment group and 1 control group). The study is designed as a virtual trial in that it will be conducted, *in situ*, with home-based participants entering self-assessments via a web-enabled adaptive platform – The participants will be under the oversight of regionally based investigators who will be responsible for study conduct and the review of blinded data on a periodic basis.

Intervention Groups and Duration: The treatment regimen for this study is shown in Table 4.

Regimen	Dose	# of Participants

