Group 1	80 mg famotidine (PO) QID + celecoxib 400 mg first dose, followed by 200 mg (PO) BID for 5 days. Following this 5-day period, participants will continue their 80 mg famotidine QID treatment for an additional nine days.	659
Group 2	Matching Placebo for famotidine and celecoxib respectively – QID + BID for five days. Following this 5-day period, participants will continue to receive matching famotidine Placebo, QID, for an additional 9 days.	659

Table 4:Study Interventions

Disclosure Statement: This is a Phase 2 randomized, double-blind, placebo-controlled study to evaluate the safety and efficacy of the combination of famotidine and celecoxib as a post-exposure prophylaxis (PEP) for newly-infected for COVID-19 patients. These participants will not be hospitalized at enrollment, and all study activities will be performed at the participant's home. Investigational product and matching Placebo will be shipped directly to the participant from the Sponsor's supplier. There will be no other physical location where participants are seen. Virtual research teams will be organized by U.S. geographical region under the oversight of a Principal Investigator licensed to practice in the state(s) in which participants reside. Each site or group of affiliated sites will be required to designate at least one physical location to serve as a research facility for storage of any paper documents generated, mail correspondence or location

for inspection activity. This designated location will be listed as a research facility under Section #3 of Form FDA 1572.

Number of Participants: Approximately 1800 participants will be screened to achieve 1465 randomly assigned to study intervention and at least 1318 evaluable participants for an estimated total of 659 evaluable participants per group.

Study Design: The study design is shown schematically in Figure 1.

Schedule of Assessments: The participants will have responsibility for entering self-assessment of symptom severity, body temperature, blood oxygen concentration (spO2) using Sponsor-supplied devices, using the web-based platform. The study Schedule of Assessments is shown in Table 5.

LEAP-CT as a Post-exposure Prophylaxis for Newly-infected COVID-19 Patients

Version 2.0; 11 April 2022

Table 5:Schedule of Assessments

Study Activities and Assessments	Screening & Randomization ¹		Treatment	Period		Observ	ation Period ²
Visit Number ³	1	2	3	4	5	6	7

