1.4. Objectives and Endpoints

Study Description: This study (LDOS-21-001-02) is a virtual Phase 2 randomized, placebocontrolled, double-blind study to evaluate the safety and efficacy of the combination of famotidine and celecoxib as a PEP for newly-infected COVID-19 patients. This study is designed to test the efficacy and safety of combinations of two well-understood agents: famotidine and celecoxib. Each of these agents separately demonstrate clinical activity in mitigating COVID-19 disease symptoms or severity, and each of which appear to have separate and complementary mechanisms of action. Qualifying patients will have been confirmed COVID-19 – positive, and have symptoms of WHO Ordinal Scale levels \leq 3, and will be randomly assigned, in a 1:1 ratio, to one of two regimens, with 659 participants per group, as follows:

• **Group 1 (Study Product)**: 80 mg famotidine (PO) QID + celecoxib 400 mg first dose, followed by 200 mg (PO) BID for 5 days. Following this 5-day period, participants will continue their 80 mg famotidine QID treatment for an additional nine days.

• Group 2 (Reference Comparator): Matching Placebo for famotidine and celecoxib respectively, QID + BID for five days. Following this 5-day period, participants will continue to receive matching famotidine Placebo, QID, for an additional 9 days.

There will be a subsequent follow-up period of 90 days from Baseline.

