7.2. Sample Size Determination

The sample size was estimated assuming that an interim analysis with stopping criteria for futility will be performed after 50% of participants have a primary endpoint assessment at Day 30. The O'Brien-Fleming beta-spending function is used to determine the non-binding futility boundary.

A total of 1318 evaluable participants, defined as part of the Full Analysis population (659 per group) are required to detect a relative reduction in the primary efficacy parameter of 60% in the active treatment arms compared to placebo (from of 6% in the placebo group to 2.4% in the active groups) with 90.0% power and using a two-sided χ^2 -test with 0.5% significance level, assuming variances are pooled, and that continuity correction was not used. Assuming a 10% screen failure rate, 1465 enrolled participants will be required.

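### The protocol gives two numbers to randomise, 1318 (659 per group) and 1465, and only 1465 allows for participants lost between randomisation and first dose

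*Protocol*

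**What the plan says.** The protocol attaches different numbers to random assignment.

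- **659 per group, 1318 in total.** Section 1.4 describes participants as "randomly assigned, in a 1:1 ratio, to one of two regimens, with 659 participants per group". The Study Description in the synopsis (Section 1.1) has the same figure: "to one of two regimens, with 659 participants per group, as follows". Table 4 lists 659 as the number of participants for each regimen. The Statistical Methods paragraph of the synopsis is in line with this for both arms: "The study will aim to enroll up to 1465 participants, which assumes a 10% screen failure rate, with a final allocation of 659 participants".
- **1465 in total.** Number of Participants in the synopsis reads: "Approximately 1800 participants will be screened to achieve 1465 randomly assigned to study intervention", and continues with "at least 1318 evaluable participants for an estimated total of 659 evaluable participants per group".

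Section 7.2 defines the 1318 evaluable participants through the Full Analysis population and adds: "Assuming a 10% screen failure rate, 1465 enrolled participants will be required". Table 8 defines the Full Analysis set as participants who were randomised and took at least one dose.

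The terms that link these figures are not used consistently:

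- Enrolment means signing the consent form in inclusion criterion 2 (Sections 1.1 and 3.2). In Table 8 the Enrolled population consists of randomised participants.
- Section 3.1 uses screen failure for people who do not meet the entry criteria and refers to the Master Protocol for the definition. Table 8 applies the term to randomised participants who stop before first intake. Section 5.2 applies it to participants found ineligible at Baseline, which comes after randomisation.

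**The concern.** Sites, drug supply and the randomisation system need one number at which randomisation ends. Someone working from Section 1.4 or Table 4 would take it to be 1318. Someone working from Number of Participants would take it to be 1465.

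The choice matters because the sample size is required in the Full Analysis set, and this design has a gap between randomisation and entry to that set. Randomisation and shipment happen at screening (Section 5.1). First intake may follow some days later (Table 5, footnote 4). Eligibility is checked again at Baseline (Section 5.2). Anyone lost in that interval is randomised but not in the Full Analysis set. A target of 1318 randomised leaves no allowance for them.

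The interim analysis at 50% of participants also depends on which total is meant: 0.5 × 1318 = 659, or 0.5 × 1465 = 732.5.

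**Working it through.** **Inputs.** Event rates are 6% on placebo and 2.4% on active treatment (Sections 1.1 and 7.2). The test is a chi-square with pooled variance and no continuity correction (Sections 7.2 and 7.4.2), with 1:1 allocation. Alpha is two-sided 5% (Sections 1.1 and 7.4.3). Section 7.2 prints 0.5%, which would need 1036 per group and cannot be the basis of 659. Target power is 90%. The 10% allowance is in Sections 1.1 and 7.2.

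**Step 1: reproduce 659.** With mean rate 0.042:

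n = [1.960 × √(2 × 0.042 × 0.958) + 1.282 × √(0.06 × 0.94 + 0.024 × 0.976)]² / 0.036²

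= [1.960 × √0.080472 + 1.282 × √0.079824]² / 0.001296, which is 651 per group after rounding up.

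The protocol's 659 is within 3% of this, and the interim futility look plausibly explains the difference (Step 5).

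**Step 2: reproduce 1465.** 2 × 659 = 1318, and 1318 / 0.9 = 1464.4, rounded up to 1465. The arithmetic is right. The 10% is exactly the gap between 1465 and 1318: 1465 − 1318 = 147, and 147 / 1465 = 10.0%.

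**Step 3: locate that gap.** Under Number of Participants, 1465 is the randomised count and 1318 the evaluable count, so the 10% falls after randomisation and before dosing. The loss before randomisation is separate: 1800 − 1465 = 335, and 335 / 1800 = 18.6%.

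**Step 4: power if randomisation stopped at 1318.** With n analysed per group,

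power = Φ{[0.036 − 1.960 × √(0.080472 / n)] / √(0.079824 / n)}.

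| Lost before first dose | Analysed per group | Power, without futility look |
|---|---|---|
| 0% | 659 | 90.4% |
| 1% | 652 | 90.1% |
| 2% | 645 | 89.8% |
| 5% | 626 | 88.9% |
| 10% | 593 | 87.2% |

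If 1465 are randomised and 10% are lost, 1465 × 0.9 = 1318.5 remain, or 659 per group, and power is 90.4%.

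**Step 5: allow for the futility look.** I assumed a standard O'Brien-Fleming-type beta-spending function at half the information, which spends about 0.020 of the 0.10 beta, and assumed that the bound is followed. Power is then 89.8% at 659 per group and 86.7% at 593. This does not use the numerical bound printed in Section 7.4.3, which is a separate matter. With the look included, 659 per group has no slack to absorb pre-dose losses.

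**The case against.** **The 1465 is the clear target.** The paragraph headed Number of Participants gives screened, randomised and evaluable counts separately. The total 1318 is printed only with the word evaluable. The 659 in the Study Description, Section 1.4 and Table 4 could be loose description of the regimens, and 'final allocation' in Statistical Methods could mean what remains after losses. This stands in part: it shows which figure was probably intended. It does not remove the conflict, because the Study Description and Section 1.4 both tie 659 per group to random assignment.

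**The 10% and the 1800 screened.** A reader might infer that a 10% screen failure rate contradicts 1800 screened for 1465 randomised, which is an 18.6% loss. On the ordinary meaning of the term it would: 10% would need 1465 / 0.9, or about 1628, screened. The document does not support that as a contradiction. Table 8 and Section 5.2 use screen failure for randomised participants who never take or never continue with study drug. On that usage 1800 to 1465 to 1318 is coherent, with two different losses at two stages. What remains is that one term covers both losses, and that 'enrolled' shifts between consent and randomisation.

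**The power loss is conditional and modest.** This is correct. It requires randomisation to stop at 1318 and participants then to be lost before dosing. At 1% loss the fixed design still has 90.1%, and at 10% the shortfall is 2.8 points.

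**The interim sample-size check could repair it.** Section 7.4.3 allows an increase if the treatment difference falls by more than 10%. That trigger concerns the size of the effect, not a shortage of dosed participants, so it does not cover this case.

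**Conclusion.** The concern holds as an inconsistency in a design number. The protocol gives both 1318 and 1465 as the number randomly assigned, 147 apart. Only 1465 is consistent with Section 7.2, which needs 659 per group in a set that requires a dose.

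A reader might go further and conclude that the trial will miss its stated power, or that the sample-size arithmetic is wrong. Neither follows. The inflation from 1318 to 1465 is correct, and randomising 1465 with a 10% loss delivers the planned 659 per group. The fall from 90.4% to as low as 87.2% arises only if 1318 is taken as the stopping number and the protocol's own 10% is then lost before dosing.

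These figures assume 6% versus 2.4%, two-sided 5% and equal loss in both groups, before the futility look. The actual pre-dose loss is unknown, so the range from 1% to 10% is the honest statement of size. The correction is worth making because it concerns a number on which the trial runs and costs almost nothing.

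**What to change.** State one participant flow wherever numbers appear:

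- about 1800 screened, with about 19% lost before randomisation;
- 1465 randomised, about 732 to 733 per group;
- 10% randomised but not dosed;
- 1318 in the Full Analysis set, 659 per group.

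Change the Study Description and Statistical Methods paragraphs of the synopsis, Table 4 and Section 1.4 so that 659 is the evaluable number per group and not the number assigned.

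Give 'enrolled' and 'screen failure' one meaning each, and apply it in inclusion criterion 2 (Sections 1.1 and 3.2), the Statistical Methods paragraph, Section 5.2, Section 7.2 and Table 8. Use a separate name for loss between randomisation and first dose. Changing the label only in the sample-size text would leave Section 5.2 and Table 8 in conflict with it.

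The cost is wording only. Every count is already in the protocol, and neither the sample size nor the analysis changes.

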1.2. Background

Refer to the Master Protocol (LDOS-21-001) for a comprehensive background discussion. For this study, a secure, adaptive, interactive source data collection platform, will be used. Because the platform is web-enabled, it provides a means for real-time data collection by the participant or study staff through any device that can access the internet.

1.3. Benefit/Risk Assessment

More detailed information about the known and expected benefits and risks and reasonably expected adverse events of each of the investigational products may be found in the Package Insert for famotidine and celecoxib respectively, and are provided in the Investigator's Brochure.

Refer to the Master Protocol (LDOS-21-001) for overall discussion of Benefit/Risk. The factors discussed here are specific to this study in home-based patients. Table 6 details the potential benefits, risks, and mitigations associated with study participation.

Factors	Discussion	Evidence and uncertainties
Analysis of condition	COVID-19 Progression	Patients with COVID-19 disease can present with a range of mild-to-severe non-specific clinical signs and symptoms, which develop two-to-fourteen days after exposure to SARS-CoV-2. These symptoms include cough or shortness of breath, and at least two of the following: fever, chills, repeated rigor, myalgia, headache, oropharyngitis, anosmia, and ageusia. More severe symptoms warranting hospital admission include difficulty breathing, a persistent sense of chest pain or pressure, confusion or difficulty to arouse, as well as central cyanosis. Of hospitalized patients, 33% develop Acute Respiratory Distress Syndrome (ARDS), the most common cause for admission to the ICU; approximately 28% of patients admitted to the ICU will die
Current Treatment Options	Only one pharmacological agent (remdesivir) has been FDA-approved for the treatment of hospitalized COVID- 19 patients.	Currently, there is no FDA-approved therapy for treating the early symptoms of COVID-19 and mitigating disease progression. Clinical management consists of supportive care, including ventilation in case of respiratory failure. Remdesivir and dexamethasone are not applicable treatment options for this outpatient study.
Benefit	Famotidine and Celecoxib have shown efficacy alone, and in (limited) combination, against viral mechanisms.	As noted in the Master Protocol, each of the two drugs in the combination therapy have been approved by FDA and are available either OTC or by prescription. Published reports indicate that each may independently act to reduce the morbidity and mortality associated with host responses to SARS-CoV-2 infection in those patients that develop COVID-19.

Table 6:Benefits, Risks, and Mitigations

Factors	Discussion	Evidence and uncertainties
Risk	Study treatments (IP) in combination and at proposed dosages and regimens.	The two investigational products have a long history of use as both prescription and over-the-counter products. They have demonstrated acceptable safety profiles in their labelled indications and usage.
		There are limited data available, to-date, of the proposed investigational products in combination, and at the proposed dosages and regimens for the proposed indication. However, there are studies of famotidine (400 mg PO) and celecoxib (200 mg PO, BID) in combination against COVID-19 in 61 patients (Personal communication from 15 March 2021). These have shown only small incidences of adverse events (one patient hospitalized and one incidence of allergic reaction in the former study).
Risk Management	Study Treatment	If intolerable side effects occur during the study, participants will be withdrawn from the trial in the participant's best interest. Patients with a history of allergic reactions or other significant uncontrolled medical conditions will be excluded from the study. In the event of adverse events or reactions, trained health professionals at the study site will take the appropriate measures for treatment, advice, or withdrawal from study.
	Study procedures	Patients will be carefully screened for any exclusion criteria to any of the planned study procedures, and will be excluded if the procedure is deemed to pose unacceptable safety risks to the patient.
	Safety Oversight	An independent DSMB will monitor the study progress for trends indicating unfavorable risk or safety profile.

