3.9. Dose Modification

Dose modification from the specified study regimens will be required if any of the following occur after the administration of study drugs:

- a participant's glomerular clearance (GFR) drops to <60 mL/min without developing QT prolongation or CNS AEs (i.e., delirium, hallucinations, disorientation, or seizures) after the results from their weekly laboratory results have been obtained by the investigator; or
- a QT wave prolongation is registered on their mobile ECG monitor; or
- a central nervous system (CNS) AE (i.e., delirium, hallucinations, disorientation, or seizures) is reported by the subject.

If any of the above occur, then the investigator will instruct the participant to stop all scheduled study medications.

For those participants with a drop in GFR and no QT prolongation or CNS AEs, they may resume study medications after testing demonstrates the GFR is >60 mL/min. Upon resolution, study drugs can be added back in stepwise fashion, e.g., BID, then TID, and finally QID. All missed or withheld doses will be noted in

For participants that had a QT prolongation or CNS AE (i.e., delirium, hallucinations, disorientation, or seizures), study medication will be permanently stopped and they will be followed for safety for the remainder of their study participation (Day 90).

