4. DISCONTINUATION OF STUDY INTERVENTION AND PARTICIPANT DISCONTINUATION/WITHDRAWAL

4.1. Discontinuation of Study Intervention

Discontinuation of study intervention and participant discontinuation/withdrawal are addressed in the Master Protocol (LDOS-21-001).

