4.2. Participant Discontinuation/Withdrawal from the Study

A discussion of participant discontinuation or withdrawal from the study is provided in **Section 5** of the Master protocol (**LDOS-21-001**).

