5. STUDY ASSESSMENTS AND PROCEDURES

Study procedures and their timing are summarized in the SoA (Table 5). Protocol waivers or exemptions are not allowed. Immediate safety concerns should be discussed with the Sponsor immediately upon occurrence or awareness to determine if the participant should continue or discontinue study intervention. Adherence to the study design requirements, including those specified in the SoA, is essential and required for study conduct.

Procedures conducted as part of the participant's routine clinical management (e.g., blood count) and obtained before signing of the ICF may be utilized for Screening or Baseline purposes, provided the procedures met the protocol-specified criteria and were performed within the time frame defined in Table 5.

Regulatory, Ethical and Study Oversight Considerations are provided in **Appendix 1** of the Master Protocol.

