7.3. Populations for Analyses

For purposes of analysis, populations are defined in Table 8.

Population	Description
Enrolled	All participants that have signed the Informed Consent Form, met the eligibility criteria, were randomized to study intervention, discontinued before first intake (Screening failures) or received at least one of study medication (Intent-To-Treat (ITT), Safety)
Full Analysis (FAS)	All participants who were randomized and received at least one dose of study medication. Participants in the FAS/ITT will be analyzed as randomized.

Table 8:Analysis Populations

Population	Description
Per Protocol (PP)	All participants who were included in the ITT, completed at least the 30-day assessments, and had no major protocol deviations that could have an influence on the primary efficacy endpoint. Participants in the PPS will be analyzed as treated.
Safety	All participants randomly assigned to study intervention and who take at least one dose of study intervention. Participants will be analyzed according to the intervention they actually received.

Participants excluded from the analysis sets mentioned above will be determined during the Blinded Data Review (BDR) and reasons for exclusions will be documented in the BDR report.

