7.4.2. Efficacy Analyses

The **primary efficacy** endpoint, the percentage of patients with at least one COVID-19–related medically attended contact, due to increased symptom severity or death (all-cause mortality) through Day 30, will be analyzed using a two group χ^2 test with pooled variances and no continuity correction. Statistics and the associated 95% confidence interval will be provided. The primary efficacy analysis will be performed using the ITT and will be repeated for robustness purposes with the PP.

In case of missing data of the primary endpoint at day 30 (Visit 4), the primary analysis will consider participants (with missing primary endpoint data until day 30) as having at least one medically attended visit. For sensitivity purposes, the primary efficacy analysis will be repeated by excluding participants with missing primary endpoint until day 30 (Complete Case Analysis).

The **secondary safety endpoints**: Incidence of Related Serious Adverse Events (SAE), Incidence of discontinuation due to related SAE and Incidence of death will also be analyzed using a χ^2 test. Descriptive statistics including exploratory confidence intervals/p-values will be provided.

All **other efficacy endpoints** will be analyzed in an exploratory manner by applying appropriate statistical methods (e.g. χ^2 test for incidences, log rank test and Kaplan Meier method for cumulative incidences, ANOVA for continuous variables) using the FAS set. Descriptive statistics including exploratory confidence intervals/p-values will be delivered.

All **other safety related endpoints** will be analyzed in a descriptive way by providing descriptive statistics and/or shift tables from baseline to the assessment visits.

For more details of the statistical analysis, methods/models refer to the SAP.

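### Table 6 withdraws participants with intolerable side effects from the trial, whereas the operative stop-drug rules keep them in follow-up; followed literally, it could turn tolerability stops into imputed primary events

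*Protocol*

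**What the plan says.** Section 1.3, Table 6 (Risk Management row) states: "If intolerable side effects occur during the study, participants will be withdrawn from the trial in the participant's best interest". A later sentence in the same cell says that, for adverse events or reactions, "trained health professionals at the study site will take the appropriate measures for treatment, advice, or withdrawal from study". Neither sentence mentions stopping the drug while the participant stays in the study.

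Two other sections treat stopping drug and leaving the study as different things:

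- **Section 3.9**, after QT prolongation or a CNS adverse event: "study medication will be permanently stopped and they will be followed for safety for the remainder of their study participation (Day 90"). After a fall in GFR alone, the drug is held and may be resumed.
- **Section 3.8.1**, when a participant is hospitalised or needs oxygen and dexamethasone is to be used: study medication is stopped first, the participant counts as a clinical failure, and follow-up for outcome continues.

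Three places only hint at the distinction:

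- **Section 5** says that immediate safety concerns are discussed with the sponsor "to determine if the participant should continue or discontinue study intervention".
- **Section 4.1** reads "Discontinuation of study intervention and participant discontinuation/withdrawal are addressed in the Master Protocol".
- **Section 4.2** reads "A discussion of participant discontinuation or withdrawal from the study is provided in" Section 5 of that same Master Protocol.

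Two analysis rules decide the consequence. The Full Analysis Set (Section 7.3, Table 8) is "All participants who were randomized and received at least one dose of study medication". When the Day 30 endpoint is missing, the primary analysis "will consider participants (with missing primary endpoint data until day 30) as having at least one medically attended visit" (Section 7.4.2), with a complete-case analysis as sensitivity.

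**The concern.** Stopping a drug and leaving a trial are separate decisions. A participant who cannot tolerate the tablets can stop them and still report whether a medically attended contact occurred by Day 30. Table 6 merges the two decisions and does so in mandatory wording.

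In many trials that would only cost some data. Here a missing Day 30 endpoint counts as an event, so a tolerability stop could enter the primary comparison as COVID-19 worsening. The planned event rates are low (6% and 2.4%), so a handful of imputed events is not negligible. Equal withdrawals in the two arms dilute the difference. Unequal withdrawals bias it: against the active arm if they are commoner there, and in its favour if they are commoner on placebo.

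**Working it through.** **1. Which rule applies to which event**

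| Event | Explicit rule shown | What happens to the participant |
|---|---|---|
| QT prolongation or CNS event | Section 3.9 | Drug stopped for good, followed for safety to Day 90 |
| GFR fall alone | Section 3.9 | Drug held, may resume |
| Hospitalisation or oxygen need, before dexamethasone | Section 3.8.1 | Drug stopped, outcome follow-up continues |
| Any other intolerable effect | Table 6 only | Leaves the trial |

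For the first three rows the specific section would reasonably prevail over a summary table. The gap is the last row.

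**2. How a withdrawal becomes an event.** A participant who took at least one dose is in the Full Analysis Set. If that participant is withdrawn before Day 30 with no earlier event, and nobody collects the outcome afterwards, the endpoint is missing and Section 7.4.2 scores it as an event.

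**3. The plan's own sample size.** Inputs are 6% versus 2.4%, 90% power and a pooled χ² test without continuity correction (Section 7.2), with two-sided 5% (Synopsis and Section 7.4.3; Section 7.2 prints 0.5%, which would need 1036 per group). The standard formula gives 651 per group against the stated 659, a small excess that the futility look could explain. Also 1318 / 0.90 = 1465, as stated.

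Power at n per arm = Φ[(d√n − 1.96√(2p̄(1−p̄))) / √(p₁(1−p₁) + p₂(1−p₂))], where d = p₁ − p₂ and p̄ is the mean of the two rates.

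With n = 659: d√n = 0.036 × 25.67 = 0.924; 1.96 × √0.0805 = 0.556; denominator √0.0798 = 0.2825. So Φ(1.303) = 90.4%.

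**4. Effect of imputed events.** Let w be the share of an arm withdrawn before Day 30 for intolerable effects. It is assumed, because the Protocol gives no rate. Take withdrawal as independent of outcome, and let participants off drug keep their arm's true rate. The analysed rate is then p′ = p + (1 − p)w.

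For 1% in each arm (0.01 × 659 ≈ 7 participants):

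- placebo 0.06 + 0.94 × 0.01 = 6.94%
- active 0.024 + 0.976 × 0.01 = 3.38%
- d√n = 0.0356 × 25.67 = 0.915; 1.96 × √0.0978 = 0.613; denominator √0.0972 = 0.312
- Φ(0.968) = 83.4%

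| Assumed withdrawal, placebo / active | Analysed rates | Power |
|---|---|---|
| 0 / 0 | 6.00% / 2.40% | 90.4% |
| 0.25% / 0.25% (about 2 per arm) | 6.23% / 2.64% | 88.7% |
| 1% / 1% | 6.94% / 3.38% | 83.4% |
| 0 / 1% | 6.00% / 3.38% | 61.6% |
| 1% / 0.5% | 6.94% / 2.89% | 92.6% |

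The table treats every withdrawal as avoidable, so the changes from 90.4% are upper bounds on what rewording could undo.

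**5. What rewording would recover.** If half of those withdrawn would refuse follow-up anyway, the 1% / 1% case becomes 0.5% / 0.5%, with power 86.9%. The gain is then 86.9 − 83.4 = 3.5 points, not 90.4 − 83.4 = 7.0.

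**The case against.** The strongest reply is that Table 6 is a benefit/risk summary, not a procedure, and that its later sentence leaves the site room for judgement. Where the addendum does set stop-drug procedures, it keeps people in follow-up, and a site would look there and in the Master Protocol first. Section 5.7.3 also requires active follow-up after an adverse event report, although it does not secure the Day 30 outcome. All this stands, and it lowers the importance. It does not remove a sentence saying what will happen to a participant for whom no other explicit rule is shown.

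A second reply is that the Master Protocol may already require outcome collection after discontinuation. That cannot be checked here, so the consequence has to stay conditional.

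A third is that the loss comes from the missing-equals-event rule and is covered by the complete-case analysis. The rule is indeed the mechanism, and the interim analysis excludes missing cases. But the complete-case analysis only shows how far the imputation drives the result; it does not recover the outcomes.

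Three stronger readings are tempting and are not supported:

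- A reader might infer that Sections 4 and 5 contradict Table 6 outright. Section 4 offers headings and deferrals, and Section 5 one general sentence. The substantive contrast is with Sections 3.8.1 and 3.9, and Section 3.9 speaks of follow-up for safety, not for the primary outcome.
- A reader might infer that the primary analysis will be biased against the active arm. No rates by arm are given, and the assumed cases run from 62% to 93% power, the last above the planned value.
- A reader might infer that the daily reporting in Table 5 already captures the endpoint. That row covers symptoms, SpO2 and temperature; Table 5 has no row for medically attended contacts.

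**Conclusion.** The mismatch is real but narrow. It concerns intolerable effects other than those handled in Sections 3.8.1 and 3.9. Harm follows only if sites act on Table 6 literally and the Master Protocol does not keep collecting outcomes after withdrawal.

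Under those conditions some tolerability stops would be counted as primary events. The illustrative cost is about 7 points of power at 1% per arm, if every case is avoidable, and under 2 points at 0.25% per arm. Unequal withdrawals could move the result either way. All of these figures rest on assumed withdrawal rates.

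Importance is minor; this is a cheap improvement.

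**What to change.** In Table 6:

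- Replace the instruction to withdraw the participant with a statement that *study medication will be stopped*.
- Add stopping study medication to the measures listed in the later sentence.
- State that dosed participants who stop drug remain in follow-up, with medically attended contacts and vital status ascertained at the Day 30 remote visit, unless they withdraw consent for follow-up.

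The Day 30 visit is already in Table 5. Name the outcome questions explicitly, because the daily entries alone do not show the primary outcome. Check the wording against Section 5 of the Master Protocol.

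Which side effects lead to stopping remains a clinical decision. The change does not touch the missing-equals-event rule or other causes of missing data.

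The cost is a wording amendment, with no new visits. The small downside is a few more remote contacts with participants who are off drug.
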